*Strategies to Augment Ketosis:
Optimization of Ketone
Delivery(STAK:OK'd)*

The Ohio State University

IRB Approval July 26, 2022

IRB# 2022H0160

Strategies to Augment Ketosis: Optimization of Ketone Delivery (STAK: OK'd) IRB Protocol

Title: Optimization of Ketone Delivery

Short title: STAK-OK'd

PI: [name], RD
Professor, Department of Human Sciences
The Ohio State University
[name]
[name]
Office: [contact] | [contact]

Co-PI: [name], DPhil
Lead Translational Scientist
The Buck Institute for Research on Aging
[name]
[name]
Office: [contact] | [contact]

ABBREVIATIONS

AcAc	Acetoacetate
BHB	Beta hydroxybutyrate
KE	Ketone ester
BDO	(R)-1,3 Butanediol
BTQ	Beverage tolerability questionnaire
LBM	Lean body mass
LC-MS	Liquid chromatography – mass spectrometry
VO ₂	Oxygen uptake
VCO ₂	Carbon dioxide release
GRAS	Generally recognized as safe
AUC	Area under the curve
C _{max}	Maximal concentration
C _{min}	Minimal concentration
T _{max}	Time of maximal concentration
T _{min}	Time of minimal concentration
mL	milliliters
mg	Milligrams
h	Hour
ANOVA	Analysis of variance
AE	Adverse event
USG	Urine Specific Gravity

STUDY SYNOPSIS

Study Title	Optimization of Ketone Delivery
Short Title	STAK-OK'd
Study Design	Open label, randomized, placebo controlled, 9-arm cross over
Study Participants	
 • Healthy men, aged 20 -30 years old, BMI between 18 and 29 kg/m²
Planned Sample Size	An evaluable sample of 12 participants/group is required; to allow for 20% attrition a final sample size of 15 is planned.
Study Products	
 1. BHB Mono-ester 2. C6 Ketone Di-ester 3. AcAc Di-ester 4. (R)-1,3 butanediol 5. Control 
All study products are generally recognized as safe (GRAS) food ingredients.

Serving Sizes	
 1. 180 mg/kg of lean body mass 2. 360 mg/kg of lean body mass
Planned Study Period	September 2022 – September 2023
OUTCOMES	
Primary	Difference in total plasma ketone appearance (AUC) between the two serving sizes of study products and control.

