bowel disease, irritable bowel syndrome, chronic constipation, severe constipation (in the opinion of the Investigator), history of frequent diarrhea, history of surgery for weight loss, gastroparesis, systemic disease that might affect gut motility according to the Investigator, medication managed reflux and/or clinically important lactose intolerance].

- Participant has a condition the Investigator believes would interfere with his ability to provide informed consent, comply with the study protocol, which might confound the interpretation of the study results, or put the participant at undue risk.

Sample Size. Our primary outcome goal is to demonstrate significant differences between serving sizes of exogenous ketone compounds in plasma total ketone AUC. Previous work using the BHB Monoester compared to ketone salt products demonstrated that a sample size of 12 participants was required to detect a difference in BHB AUC of ~20% (80 mM.h⁻¹) between ketone compounds with alpha set at 0.5 and power at 0.8. This sample size will also give sufficient power to address our secondary aims which include differences in peak ketone concentrations, plasma BHB, AcAc, breath acetone, glucose, insulin, free-fatty acids, amino acids, blood chemistry, pH, gas exchange values and heart rate. Based upon prior studies, we expect up to 20% of participants will withdraw from the study after recruitment, and therefore we will plan to recruit 15 participants.

Recruitment:

Recruitment will occur through well-established methods at OSU, which include word of mouth, ResearchMatch database, social media engagement and flyers. For this study we will specifically aim to recruit cadets in the OSU Reserve Officers Training Corps (ROTC), who have participated in research on ketosis in the past and been supported by their cadre to enroll in our research projects (see letters of support from Army, Navy, and Air Force ROTC leadership).

Randomization:

If a participant meets all inclusion and none of the exclusion criteria, the following will occur at the end of the screening visit:

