Statistical Plan. Statistical analysis of data will take place on completion of the study in collaboration with Buck Bioinformatics Core. Participant data will be included if they have completed at least 2 serving sizes of one exogenous ketone product AND the control Test Days (i.e., BHB- mono-ester 180 mg/kg, BHB mono-ester 360 mg/kg and Control). Any incomplete exogenous ketone compounds (i.e., participant completed C6 Di-ester 180 m/kg and AcAc ester at 360 mg/kg) will be excluded from the analysis. All decisions regarding exclusion from the analysis population will be documented prior to database lock. Missing data will not be imputed, and only observed data will be included in the statistical analysis.

Repeated measure group x time ANOVA (or a non-parametric alternative) will be performed following initial tests to ensure sphericity is not violated. We will compare data between control group vs. each individual exogenous ketone at both doses (i.e., control vs BHB-mono ester (180 mg/kg) vs BHB-mono-ester (360 mg/kg). We will also test for condition x time interactions. If significance is detected, post-hoc comparisons will be made using Tukey's HSD tests (or non-parametric alternative) to correct for multiple comparisons. Significance will be accepted at an alpha level of P < 0.05.

Other data processing:

- Area Under the Curve (AUC) will be calculated using the Trapezoid Rule.
- Maximal/minimal concentration data (C_{max} and C_{min}) and time of maximal/minimal concentration (T_{max} and T_{min}) will be extracted from the raw data.

- A composite tolerability score is calculated by adding the scores (0 -3, corresponding to none, mild, moderate, severe) of all ten listed symptoms.

STUDY MONITORING

Concomitant Medication/Supplements and Treatment

All concomitant medications/supplements used 1 months prior to Screening Visit and during the study will be reported to the study personnel for assessment and recorded in the participant's study documents.

Adverse Event Monitoring

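### The power of 0.8 quoted for n = 12 is not the power of the omnibus-plus-Tukey rule that decides the 180 vs 360 mg/kg contrast; for three conditions the Tukey step can be dropped or the power restated

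*Protocol*

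**What the plan says.** The Protocol's Sample Size paragraph (under Participants) sets the primary goal as showing differences between serving sizes in plasma total ketone AUC. It takes its number from previous work, in which "a sample size of 12 participants was required to detect a difference in BHB AUC of ~20% (80 mM.h⁻¹) between ketone compounds". The error rate and power follow: "between ketone compounds with alpha set at 0.5 and power at 0.8". No test, SD, sidedness, within-person correlation or multiplicity adjustment is given. The Synopsis repeats the target: "An evaluable sample of 12 participants/group is required; to allow for 20% attrition a final sample size of 15 is planned".

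The Statistical Plan (under Data Analysis and Statistical Methods) fixes the decision rule. Each product is analysed with three conditions: "We will compare data between control group vs. each individual exogenous ketone at both doses". Pairwise tests come second, only if the omnibus test is significant, and use Tukey's "HSD tests (or non-parametric alternative) to correct for multiple comparisons. Significance will be accepted at an alpha level of P < 0.05".

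**The concern.** The Protocol fixes both a power and a decision rule, and the two do not match. Nothing in the Sample Size paragraph allows for the omnibus test or for Tukey, yet the serving contrast is declared significant only after both. A reader will take 0.8 as the chance of detecting a difference of the quoted size under the stated analysis, and the Protocol does not show that.

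The adjustment is also unnecessary where it costs most. AUC yields one value per test day, so each product has exactly three conditions and no time factor. In that case a significant three-condition test followed by unadjusted pairs is a closed procedure. If control truly differs from both servings, the only null hypothesis that can still be true is equality of the two servings, and one test at 0.05 covers it. The Sample Size paragraph also claims adequate power for a long list of secondary outcomes, many of which would meet the same rule.

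**Working it through.** **Inputs.** From the Protocol: n = 12 evaluable, power 0.8, difference about 20% (80 in the Protocol's AUC units), three conditions per product, analysis threshold 0.05, dropout 20%. Assumed: the intended alpha is two-sided 0.05, the quoted power belongs to a paired t-test, and sphericity holds.

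**Step 1: the plan's own figure.** n = 12 cannot be reproduced, since no SD or test is given. Instead, solve for the effect that would make it true. With 11 df the critical t is 2.201. Power 0.80 from the noncentral t needs noncentrality 3.078, so the standardised paired difference is dz = 3.078/√12 = 0.889. The implied SD of the differences is 80/0.889 = 90. The recruitment figure does reproduce: 12/0.8 = 15.

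**Step 2: the same effect under Tukey.** Pooled repeated-measures error has (3 − 1)(12 − 1) = 22 df. The studentised range point is q(0.95; 3, 22) = 3.553.
- Critical t = 3.553/√2 = 2.512, against 2.074 unadjusted.
- Per-pair p = 0.0198.
- Power at noncentrality 3.078 = **0.711**.
- With each contrast on its own 11 df: critical t 2.701, power 0.650.

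**Step 3: what would restore 0.8 under Tukey.** dz must rise to 0.976, a ratio of 0.976/0.889 = 1.10, so about 20% becomes about 22%. Alternatively, 15 evaluable participants give 0.826 (14 give 0.793). At 20% dropout that means 15/0.8 = 18.75, or 19 recruited.

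**Step 4: gate or Tukey?** Simulation (100,000 runs, n = 12, dz = 0.889), power for 180 vs 360 mg/kg:

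| Position of control | Gate + Tukey | Gate + unadjusted paired t |
|---|---|---|
| At least one effect size below the lower serving | 0.71 | 0.80 |
| Equal to the lower serving | 0.71 | 0.76 |
| Midway between servings | 0.70 | 0.71 |

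Tukey without the gate gives 0.711, so under the planned rule nearly all the loss is Tukey's.

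**Step 5: family-wise error within one product** (simulated, pooled error):

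| Truth | Gate + unadjusted pairs | Gate + Tukey |
|---|---|---|
| All three equal | 0.049 | 0.045 |
| Only the servings equal | 0.050 | 0.020 |

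Gated paired t-tests give 0.048 and 0.051 in a separate simulation of 40,000 runs. Dropping Tukey therefore keeps the error at about 5%.

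**Step 6: dependence on the assumed calibration.** Tukey power at n = 12 if the quoted 0.8 came from another calculation:

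| Source of the 0.8 | Tukey power |
|---|---|
| Pooled error, 22 df | 0.66 |
| Normal approximation | 0.62 |
| One-sided 0.05, paired | 0.56 |
| Alpha 0.5 as printed, paired | 0.17 |
| Two-sample, 12 per group; within-person correlation 0 / 0.1 / 0.3 / 0.5 | 0.66 / 0.72 / 0.83 / 0.94 |

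**The case against.** The strongest reply is that the Protocol never says its 0.8 is for a single unadjusted comparison. It reports what previous work required, and that calculation cannot be seen. A reader might infer that the design delivers 0.71 at most. The documents do not support that bound: the Synopsis speaks of 12 per group, and if the calculation was two-sample, Tukey power in this crossover passes 0.8 by a within-person correlation of 0.3. This stands, and 0.71 must be read as conditional.

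The effect may also be larger than the one quoted. The 20% is for BHB AUC between compounds, whereas the primary contrast is total ketone AUC between servings that differ two-fold. On the same calibration Tukey power is 0.80, 0.98 and above 0.99 for differences 1.1, 1.5 and 2 times the quoted one. If all 15 recruits complete a product it is 0.83 at the quoted difference. This also stands: no practical loss is shown if the true serving difference is well above 20%.

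Tukey is valid, only conservative. Closure requires a gate on the three-condition effect. The Statistical Plan describes a group by time ANOVA and also tests condition by time interactions; if an interaction opens the gate, closure does not protect unadjusted condition contrasts. That limits the argument to outcomes with one value per day, which include the primary.

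Two further inferences fail. One is that every secondary outcome suffers the same loss; the gain from dropping Tukey shrinks to almost nothing when control lies between the servings. The other is that Tukey will be run over all condition-by-time cells. The Protocol does not say so, and defining that family can be left to a statistical analysis plan.

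None of this makes the quoted power a property of the stated rule.

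**Conclusion.** The point holds in a limited form. The Protocol states power 0.8 with no adjustment and an alpha printed as 0.5, then decides the serving contrast at 0.05 through an omnibus test and Tukey, which works at about 0.020 per pair. Under a paired two-sided 0.05 reading, power at the quoted difference is about 0.71 rather than 0.80, which amounts to a detectable difference about 10% larger. This rests on alpha 0.05 being intended, on the paired calibration and on sphericity; the missing SD, test and correlation prevent a firmer figure. For outcomes with one value per day, Tukey after a significant three-condition test adds no protection needed to hold 5% within a product. It is a wording matter worth settling before analysis, not a flaw that invalidates the trial.

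**What to change.** Correct the alpha in the Sample Size paragraph so that it agrees with the Statistical Plan. Then choose one of two routes.

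**(a) Drop Tukey where closure applies.** For AUC and other one-value-per-day outcomes, test the three conditions within a product; if significant, make the three paired comparisons at 0.05 without Tukey, and cite the three-condition closure property. State that the gate is the three-condition effect, not a condition by time interaction.

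**(b) Keep Tukey and restate the power for it,** giving the assumed test, SD and within-person correlation. The 0.71 should go in only if the source calculation proves to be a paired two-sided test at 0.05.

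Both are changes of wording, with no added participants or visits. If 0.8 under Tukey at the quoted difference is required instead, the paired calibration implies 15 evaluable and 19 recruited.

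The cost of (a) is the loss of Tukey's incidental conservatism. When only the servings are equal, error per product rises from about 2% to 5%. Across four products, treated as independent, that is 1 − 0.98⁴ = 8% against 1 − 0.95⁴ = 19%. The sponsor should say whether control within each product is what it intends.

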Participants will report to the study center in the morning of each Test Day. Compliance with pre-test instructions (fasted > 10h, no alcohol >24h, no exercise >24h, consumed pre-test food) will be confirmed by the Investigator. Participants will complete a baseline Beverage Tolerability Questionnaire (BTQ) and satiety visual analogue scale. Participants will be asked to completely void their bladder and a sample will be analyzed for hydration status. Participants with samples reading greater \geq 1.025 USG, and asked to don the Bluetooth heart rate monitor chest strap. A study team member will assist the participant with application of a continuous ketone meter into the back of the arm, this will be removed and replaced with a fresh sensor at Test Days at ~2-week intervals; the sensor will be removed 24 hours after the cessation of the last in lab testing bout. Participants will be given written instructions on how to remove and dispose of monitor. A trained member of the study team will insert an IV cannula into a vein in the antecubital fossa to allow for repeated blood sampling. The cannula will be flushed with a small volume of saline after each sample withdrawal to maintain patency. At the same time as all whole blood samples, we will also collect capillary blood samples from a finger for real-time analysis of blood BHB and glucose concentration, using lancing device, commercially available test strips and a handheld monitor (KetoMojo, CA, USA). Participants will wear a fitted facemask connected to a metabolic cart for 10 minutes to collect measures of respiratory gas exchange. Participants will exhale once into a commercially available handheld breath acetone analyzer (Readout, MI, USA). Baseline blood sample, baseline respiratory gas measures and baseline breath acetone will be collected.

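### A pre-product baseline is collected on every test day, but AUC, Cmax/Cmin and the condition main effect are analysed without it, so day-to-day fasting variation stays in the error

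*Protocol*

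**What the plan says.** **Collection.** Under Testing Days, after the compliance check and before the product is taken, the protocol states: "Baseline blood sample, baseline respiratory gas measures and baseline breath acetone will be collected". A baseline satiety scale and tolerability questionnaire are completed in the same session. One product is taken per test day, in a nine-arm crossover.

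**Derivation.** Under Other data processing: "Area Under the Curve (AUC) will be calculated using the Trapezoid Rule". Cmax, Cmin and their times are read from the raw data. No baseline subtraction, change score or baseline covariate is named.

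**Model.** The Statistical Plan names a group-by-time repeated-measures ANOVA (or a non-parametric alternative) comparing control with both serving sizes of each product, plus a condition-by-time interaction test. It does not say whether the pre-product sample is one of the levels of time, or whether AUC is total or incremental.

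**Size.** The Sample Size paragraph gives 12 evaluable participants and 15 recruited. It also claims that 12 suffice for glucose, insulin, free fatty acids, gas exchange and other secondary outcomes.

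**The concern.** A crossover removes stable differences between people. It does not remove differences between one person's test days. If someone arrives with a higher fasting value on one day than another, that difference enters the contrast between the two products.

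AUC and Cmax/Cmin are single numbers per test day, so no time factor can separate the starting level from the response. The same holds for the condition main effect in the ANOVA, which averages over time. The information needed to reduce this noise is already collected, and the stated plan does not use it for these comparisons.

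What is at stake is precision in a small trial, most plausibly for outcomes whose fasting level is large relative to the acute response, such as glucose, free fatty acids, bicarbonate or VO2.

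**Working it through.** **1. The protocol's own figures.** Dropout: 12 / (1 − 0.20) = 15, which reproduces. The 12 cannot be reproduced, because no SD or correlation is given. The Sample Size paragraph also reads "with alpha set at 0.5 and power at 0.8", whereas the Statistical Plan says "Significance will be accepted at an alpha level of P < 0.05". I take 0.05, two-sided. A paired t-test with n = 12 and 80% power then needs a standardised difference of 0.889. With the stated difference of 80, the implied SD of the paired difference is 80 / 0.889 = 90.

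A difference of 80 that is 20% of the mean implies a mean AUC of 80 / 0.20 = 400. Over about 240 min this is 400 / 240 = 1.67 mM, in line with the expected 1.5–2 mM under Serving Size Rationale. Read in hours it would be 400 / 4 = 100 mM. I therefore assume mM·min.

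**2. Where a day-level shift goes.** I simulated one data set of 12 people × 3 conditions × 7 times (residual SD 0.3) and added a constant shift for each person and day.

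| Shift SD | F, condition main effect | F, condition × time |
|---|---|---|
| 0 | 47.0 | 2.596 |
| 0.1 | 13.2 | 2.596 |
| 0.3 | 6.5 | 2.596 |

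The shift stays in the error of the main effect and cancels from the interaction. With time zero dropped from the same data (shift SD 0.1), the interaction F is again unaffected by the shift, but it is 1.31 instead of 2.596. It then compares only the shapes of the post-product curves, and an effect sustained over the post-product period moves into the main effect, where the shift remains. So the interaction gives a shift-free comparison of change from the pre-product value only if time zero is a level.

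**3. CI width with and without the covariate, n = 12.** For within-person correlation r, the width ratio is approximately √(1 − r²) × penalty. The penalty covers the lost degree of freedom and chance baseline imbalance: √(1 + 1/(df − 2)) × t(df − 1)/t(df).

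- 3 conditions: df = 11 × 2 = 22. Penalty = √(1 + 1/20) × 2.0796/2.0739 = 1.028.
- 9 conditions: df = 11 × 8 = 88. Penalty = √(1 + 1/86) × 1.9876/1.9873 = 1.006.

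| Assumed r | √(1 − r²) | 3 conditions | 9 conditions |
|---|---|---|---|
| 0 | 1.000 | 1.03 | 1.006 |
| 0.3 | 0.954 | 0.98 | 0.96 |
| 0.5 | 0.866 | 0.89 | 0.87 |
| 0.7 | 0.714 | 0.73 | 0.72 |

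Simulation with 3,000 runs per setting gives the same values to rounding.

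**4. The primary ketone AUC.** If a fasting shift with day-to-day SD s persists over 240 min, it contributes √2 × 240 × s to the SD of an AUC difference. The share of variance is that figure squared over 90². The protocol gives no s, so the values below are assumptions.

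| s (mM) | SD contributed | Share of variance | Power if fully removed |
|---|---|---|---|
| 0.02 | 6.8 | 0.6% | 80% |
| 0.05 | 17.0 | 3.6% | 81% |
| 0.10 | 33.9 | 14% | 86% |
| 0.15 | 50.9 | 32% | 92% |
| 0.20 | 67.9 | 57% | 99% |

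Full removal is an upper bound. In terms of the correlation between baseline difference and AUC difference, starting from 80% power and losing one degree of freedom, power is about 79% (r = 0), 83% (0.3), 89% (0.5) and 97% (0.7).

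**The case against.** **The plan does use baselines, through time.** A reader might infer that the analysis ignores them altogether. The protocol does not support that: a group-by-time ANOVA with an interaction test uses the pre-product value if it is a level of time, and a constant day-level shift then does no harm to that test. This stands for serial outcomes, subject to the unstated role of time zero. It does not help AUC, Cmax/Cmin or the condition main effect.

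**AUC is named only for ketones.** The outcome lists attach AUC to total and individual ketones, where fasting values are probably low and the gain small. The trapezoid line is general, but nothing says it will be applied to glucose or insulin. This stands, so the case for the secondary outcomes rests on the main effect and on Cmax/Cmin.

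**Tolerability.** A reader might infer that symptoms present before the drink are counted against the product. They are not: the Beverage Tolerability Questionnaire section says the post-beverage form asks about issues occurring since the beverage. Tolerability is no part of this point.

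**The fasting state is already standardised, and unadjusted AUC is valid.** Both are true. Fasting, alcohol, exercise and pre-test food rules reduce day-to-day variation by an unknown amount. A reader might infer bias, but randomised order keeps the unadjusted contrast unbiased; only precision is at issue.

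**An analysis plan may add a covariate.** It may. But this protocol itself fixes the derivations and names the model, and that model has no baseline term.

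**Conclusion.** The point holds as a matter of precision. For AUC, Cmax/Cmin and the condition main effect, the stated analysis leaves day-to-day fasting variation in the error although a same-day baseline is available.

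The trade is lopsided: a cost of about 3% (three conditions) or 0.6% (nine conditions) in CI width if the baseline carries no information, against a narrowing of 11–28% at correlations of 0.5–0.7. At 0.3 the narrowing is only 2–4%. All the correlations are assumptions, since the protocol gives no SD, correlation or fasting variability.

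For the primary ketone AUC the gain is probably small; it becomes material only if the day-to-day fasting SD is about 0.10 mM or more, under the unit and alpha readings above. It may be larger for secondary outcomes with a high fasting level, but the document has no figures to show this.

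**What to change.** - Analyse AUC and Cmax/Cmin in a linear mixed model with participant as a random effect and condition as a fixed effect.
- Use the same approach for the post-product values of serial outcomes (glucose, insulin, free fatty acids, bicarbonate, gas exchange, satiety), keeping time and condition-by-time in the model and allowing for correlation within a test day.
- Add the same-day pre-product value, centred on the participant's mean baseline, as a covariate, with that mean also in the model. Estimating the slope avoids the variance that plain subtraction adds at low correlation (below 0.5 when the variances are equal).
- Do not also enter time zero as an outcome level when it is the covariate. State this, and state whether AUC is total or incremental.

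**Cost.** No new data, one or two degrees of freedom, and a short rewrite of the Statistical Plan. The real change is a mixed model in place of the classical repeated-measures ANOVA, into which a covariate that varies by test day does not fit. The change should be fixed before the product codes are opened to the analysts.
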